4.5.1 Absolute Bioavailability of ALXN1210 SC

The geometric means ratio (ALXN1210 SC/ALXN1210 IV) and its 90% and 95% CI will be computed for the PK-parameters C_{max} , AUC_t, and AUC_{∞}, and will be tabulated. To calculate CIs of geometric means ratios, parameters will be log-transformed and CIs will be constructed for the mean difference of log-transformed parameters, assuming that log-transformed parameters are normally distributed and have unequal variances. The CIs are then back-transformed to receive CIs for the geometric mean ratios.

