5.1.1. Clinical Studies

ALXN1210 has been administered safely to healthy subjects in 200 mg and 400 mg intravenous (IV) doses in a single ascending dose (SAD) study (Study ALXN1210-HV-101, N = 10). Healthy subjects have also been administered multiple 400 mg and 800 mg IV doses on an every 4 week (Q4W) regimen in an ongoing multiple ascending dose (MAD) study (Study ALXN1210-HV-102, N = 12). The starting doses of ALXN1210 IV in these 2 healthy volunteer studies were selected to assess safety in healthy volunteers and to have measurable pharmacologic activity (eg, inhibition of complement activation) based on the therapeutic exposure required with eculizumab. No safety concerns have been identified in either of the Phase 1 studies, both of which were randomized, blinded, and placebo controlled. In the completed Study ALXN1210-HV-101 (SAD), no serious adverse drug reactions, treatment discontinuations, or deaths were reported.

Conclusions from Study ALXN1210-HV-101 are as follows:

- ALXN1210 exhibited prolonged pharmacokinetic (PK) exposure with mean geometric half-life estimates of 32.4 days and 30.8 days following single doses of 200 and 400 mg, respectively.
- The PK parameters (area under the serum concentration versus time curve from time zero to the last quantifiable concentration $[AUC_t]$, area under the curve from time zero to infinity $[AUC_{\infty}]$, and maximum observed serum concentration $[C_{max}]$) increased in a slightly less than dose-proportional manner over the studied range of 200 to 400 mg based on the protocol-specified statistical analysis.

- Following single 200 mg and 400 mg doses of ALXN1210 IV, all 6
 pharmacodynamic (PD) variables (total complement C5 serum concentration, free
 complement C5 serum concentration, chicken red blood cell [cRBC] hemolysis,
 classical complement pathway [CCP] activity, complement alternative pathway
 [CAP] activity, and plasma C5b-9 activity) showed dose-dependent reductions from
 baseline. The effect of ALXN1210 on these PD variables was immediately evident
 after end of infusion (EOI). At the EOI, the mean free C5 serum concentrations and
 cRBC hemolysis activity were inhibited by > 99% and > 97%, respectively.
- The duration of the effect was longer following a 400-mg dose than a 200-mg dose.
- All subjects were negative for antidrug antibody (ADA) through Day 150.

In addition, multiple doses of ALXN1210 IV have been administered to patients with PNH.

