6. STUDY OBJECTIVES AND PURPOSE

The purpose of the study is to evaluate the safety, tolerability, pharmacokinetics (PK), pharmacodynamics (PD), and immunogenicity of a single dose of ALXN1210 administered subcutaneously (SC) compared to a single dose of ALXN1210 administered intravenously (IV) in healthy subjects. Data from this study will be used to determine the absolute bioavailability of ALXN1210 SC in healthy subjects.

6.1. **Primary Objectives**

The primary objectives of this study are as follows:

- To evaluate the safety and tolerability of a single dose of ALXN1210 SC compared to ALXN1210 IV in healthy subjects, as assessed by physical examination findings, vital sign measurements, immunogenicity, laboratory analysis, and assessments of AEs.
- To determine the absolute bioavailability of ALXN1210 SC.

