8.3.2. ALXN1210 SC Dose

A single dose of 400 mg, equivalent to 4 mL, will be administered SC via 4 x 1 mL injections in the abdominal area. Administration of a single 400-mg dose of ALXN1210 SC is expected to have an acceptable safety profile. Single doses of 400 mg of ALXN1210 SC and placebo SC, administered as described in this protocol, are anticipated to provide data from which multiple dose simulations may be generated in order to project the dosing regimens necessary to achieve therapeutic serum concentrations (> 50 μ g/mL) in patients.

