18.7. Pharmacokinetic Analysis

The individual serum concentration data for ALXN1210-treated subjects, with actual sampling dates and times, will be used to derive the PK parameters by noncompartmental analyses methods using Phoenix WinNonlin 6.3 or higher.

The following PK parameters will be derived: maximum observed serum concentration (C_{max}), time to maximum observed serum concentration (T_{max}), area under the serum concentration versus time curve from time zero to the last quantifiable concentration (AUC_t) area under the curve from time zero to infinity (AUC_{∞}), terminal elimination rate constant (λ_z), terminal elimination half-life ($T_{\frac{1}{2}}$), total clearance (CL or CL/F), and volume of distribution (V_d or V_d/F).

The geometric means ratio (ALXN1210 SC/ALXN1210 IV) and its 90% CI will be computed for C_{max} , AUC_t, and AUC_{∞}, and will be tabulated. The CI will be computed using the between-subject variance. Assessments of concentration over time will be presented.

Further details will be provided in the Statistical Analysis Plan (SAP).

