4.2. Sample Size and Power

A total evaluable sample size of 36 subjects, (24 ALXN1210 SC subjects [receiving active treatment] from Cohort 1 and 12 ALXN1210 IV subjects from Cohort 2), will provide > 80% power to infer that the lower bound of a 90% confidence interval (CI) for the ratio of the bioavailability of ALXN1210 SC to IV is > 0.4, assuming an absolute bioavailability of 0.6 and a coefficient of variation (CV) of 0.35. Additionally, 6 subjects will receive placebo treatment via the SC route, including 2 in Cohort 1a and 4 in Cohort 1b. Randomization within Cohort 1a (6 subjects) will be conducted in a 2:1 ratio. After Cohort 1a, 36 subjects will be randomized in a 2:1 ratio to Cohort 1b (ALXN1210 SC or placebo SC) or Cohort 2 (ALXN1210 IV), and within Cohort 1b, subjects will be randomized in a 5:1 ratio, to receive either ALXN1210 SC or ALXN1210 SC placebo. This brings the total planned number of subjects to N = 42.

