- $\circ~$ A minimum number of 3 data points in the terminal phase will be used in calculating λ_z , with the line of regression starting at any post-C_{max} data point (C_{max} should not be part of the regression slope)
- Terminal elimination half-life $(t_{\frac{1}{2}})$
- Total clearance (CL or CL/F), calculated as dose/AUC $_{\infty}$
- Apparent volume of distribution during terminal phase (V_d or V_d/F), calculated as dose/($\lambda_z*AUC_\infty)$

All pharmacokinetic parameters will be listed for each individual subject and will be summarized by treatment group. In addition, 95% CI of the mean and geometric mean parameters will be calculated.

Some PK parameters may not be calculated for all or some subjects if the concentration data are not deemed to be amenable to evaluation. Explanations for PK parameters that could not be estimated will be provided in the clinical study report (CSR).

Additional PK parameters may be calculated, as appropriate.

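### Does the less than dose-proportional exposure seen after IV dosing make the SC/IV AUC∞ ratio at equal 400 mg doses an unsafe estimate of absolute bioavailability?

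*SAP*

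**What the plan says.** Protocol section 6 gives a main use of the data: "to determine the absolute bioavailability of ALXN1210 SC". It is also a primary objective in section 6.1.

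Protocol 18.7 plans one comparison: "The geometric means ratio (ALXN1210 SC/ALXN1210 IV) and its 90% CI will be computed for" Cmax, AUCt and AUC∞. SAP 4.5.1, whose heading is absolute bioavailability, keeps this and adds a 95% interval: "The geometric means ratio (ALXN1210 SC/ALXN1210 IV) and its 90% and 95% CI will be computed for the PK-parameters" just named. Intervals are built on the log scale with unequal variances. Both active arms receive a single 400 mg dose.

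No ratio is labelled as F. SAP 4.5 gives "Total clearance (CL or CL/F), calculated as dose/AUC"∞ for both routes, so the AUC∞ ratio is the natural reading.

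On linearity, Protocol 5.1.1 says that AUCt, AUC∞ and Cmax in the earlier single-dose IV study (HV-101, N = 10) "increased in a slightly less than dose-proportional manner over the studied range of 200 to 400 mg based on the protocol-specified statistical analysis". It also gives "half-life estimates of 32.4 days and 30.8 days following single doses of 200 and 400 mg, respectively". Neither document gives AUC values or a dose exponent.

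The sample size in SAP 4.2 is set "assuming an absolute bioavailability of 0.6 and a coefficient of variation (CV) of 0.35".

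**The concern.** For each arm, AUC∞ is the dose reaching the circulation divided by clearance. At equal nominal doses the SC/IV ratio is therefore F times (IV clearance / SC clearance), which is F only when the two clearances agree.

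At F = 0.6, about 0.6 × 400 = 240 mg reaches the circulation after SC dosing, against 400 mg after IV. Both amounts lie within 200 to 400 mg, the range over which Protocol 5.1.1 reports less than proportional exposure. Read as dose-dependent clearance, that statement puts lower clearance in the SC arm, and the ratio would overstate F.

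Such a bias would be systematic: it would not shrink with more subjects. With one dose level per route, the study's own AUC ratio could not reveal it. Neither SAP 4.5.1 nor Protocol 18.7 states the assumption or plans a check. The estimate addresses a primary objective, and Protocol 8.3.2 expects data from which "multiple dose simulations may be generated in order to project the dosing regimens necessary to achieve therapeutic serum concentrations". An inflated F could carry into those projections.

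**Working it through.** **Inputs.** F = 0.6, CV = 0.35, 24 SC and 12 IV subjects, bound 0.4 on a 90% CI (SAP 4.2, Protocol 18.3). Half-lives 32.4 and 30.8 days, with CVs 16.2% and 10.2% (Protocol 5.1.1 and 8.3.1). Assumed: AUC∞ proportional to (systemic dose)^β, with β from 0.98 to 0.85.

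**1. The plan's power figure.**
- Log-scale variance = ln(1 + 0.35²) = 0.1156.
- SE of the log ratio = sqrt(0.1156 × (1/24 + 1/12)) = 0.120.
- Power = Φ(ln(0.6/0.4)/0.120 − 1.645) = Φ(3.37 − 1.645) = 95.8%. A simulated unequal-variance interval gives 94.7%. Both meet the stated >80%.
- 90% CI around 0.60, with t(34 df) = 1.691: 0.60 × exp(±1.691 × 0.120) = 0.49 to 0.74.

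**2. Possible bias at F = 0.60.** The ratio reads 0.6^β, so the log bias is (1 − β) × 0.511.

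| β | AUC fold when dose doubles | ratio reads | relative bias | bias / SE | coverage of 90% CI |
|---|---|---|---|---|---|
| 0.98 | 1.97 | 0.606 | +1.0% | 0.09 | 90.0% |
| 0.95 | 1.93 | 0.616 | +2.6% | 0.21 | 89.3% |
| 0.90 | 1.87 | 0.631 | +5.2% | 0.43 | 87.3% |
| 0.85 | 1.80 | 0.648 | +8.0% | 0.64 | 83.8% |

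**3. Can the documents fix β?** If volume is constant, half-life is proportional to AUC∞/dose, so β = 1 − ln(32.4/30.8)/ln 2 = 0.927 (ratio 0.623, +3.8%). With an assumed 5 subjects per dose, the log half-life difference is 0.051 and its SE is sqrt((ln(1 + 0.162²) + ln(1 + 0.102²))/5) = 0.085. The difference is 0.6 SE, so the half-lives do not exclude β = 1.

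**4. Is clearance the cause?** Protocol 5.1.1 does not mention clearance, and it reports the shortfall for Cmax as well. The fraction of an IV dose eliminated during an infusion of length T is about kT/2, with k = ln 2/30.8 = 0.0225 per day. For an assumed 4-hour infusion this is 0.0225 × (4/24)/2 = 0.19%. Dose-dependent clearance therefore cannot account for lower dose-normalised Cmax. A difference between two small dose groups, in body size for example, could lower all three measures together and would not bias an SC/IV ratio here. The constant-volume assumption in step 3 also predicts proportional Cmax, contrary to the report.

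**5. Would an adjusted estimate, F = R^(1/β), be better?** (R is the observed AUC∞ ratio.) Assume β comes from 4 to 6 subjects per dose with AUC CV of 30% to 15%.
- SE(β) = sqrt(2 ln(1 + CV²)/n)/ln 2 = 0.124 (n = 6, 15%), 0.181 (n = 5, 20%), 0.299 (n = 4, 30%).
- SE of log F = sqrt((0.120/β)² + (ln R/β²)² SE(β)²). At β = 0.927 and R = 0.623 this is 0.147, 0.163 and 0.210, against 0.120 unadjusted.
- Adjustment reduces mean squared error only if the log bias exceeds sqrt(SE_adj² − 0.120²). At the most favourable SE(β), 0.124, this requires:

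| β | bias needed | bias present |
|---|---|---|
| 0.95 | 0.078 | 0.026 |
| 0.927 | 0.084 | 0.037 |
| 0.90 | 0.091 | 0.051 |
| 0.85 | 0.105 | 0.077 |

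The bias present falls short in every row, and the larger values of SE(β) widen the gap.

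**The case for a change.** The strongest opposing case is that the assumption is real, unstated and attached to a primary objective, and that stating it with one sensitivity row would cost no subjects, samples or visits. The direction needs no extrapolation at F = 0.6, and no planned analysis addresses it: SAP 4.7 is an optional exposure-response analysis, and the allowance for extra PK parameters names nothing. All of that is correct. The arm-wise half-lives, CL or CL/F and concentration profiles in SAP 4.5 give a reader something to look at, but they are descriptive.

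The power law also ignores slow SC absorption. A one-compartment model with concentration-dependent clearance and an assumed absorption half-life of 1 to 5 days gives somewhat larger bias: +2.6% to +3.4% at β = 0.95, and +8.2% to +10.6% at β = 0.85. Even in the last case R^(1/β) does not help. The unadjusted root mean squared error is sqrt(0.120² + (ln 1.106)²) = 0.157. The adjusted one, at SE(β) = 0.124 and with a residual log bias of 0.028, is 0.161.

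The most striking figures carry little weight. If F were 0.40, the chance that the lower limit passes 0.4 would rise from 5% to 10% (β = 0.95) or 30% (β = 0.85). But 0.4 × 400 = 160 mg lies below the studied range, and the SAP sets no test at 0.4; that value appears only in the sizing. Harm to regimen projection is also conjectural: Protocol 8.3.2 does not say that F will be combined with IV clearance from other doses.

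What stands is that a standard assumption goes unwritten.

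**Conclusion.** No change to the plan follows. The AUC∞ ratio at equal doses rests on equal clearance in the two arms, as this estimator always does. The evidence against that assumption is one qualitative statement from 10 subjects, and its Cmax component points away from clearance as the cause.

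If clearance were nevertheless responsible, the overstatement at F = 0.60 would be about 1% to 5% for exponents of 0.98 to 0.90. That is under half a standard error and well inside a 90% CI of about 0.49 to 0.74. An exponent of 0.85 gives 8%, but AUC rising only 1.80-fold on doubling the dose is hard to call slight. All exponents are assumptions.

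The available correction would leave the unadjusted ratio as the main result and would itself be less accurate over the whole range considered. Anyone wanting a sensitivity value can apply an exponent to the tabulated ratio. Authors of the study report can state the assumption and set the ratio beside the HV-101 dose-proportionality result and the half-lives by arm, all of which will be to hand.

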8.1. Overall Study Design

This is a Phase 1 study designed to evaluate the safety, tolerability, PK, PD, and immunogenicity of a single 400 mg dose of ALXN1210 SC compared to a single 400-mg dose of ALXN1210 IV or placebo SC in 42 healthy subjects. All subjects will be screened for eligibility in the study after providing signed and dated institutional ethics committee-approved written informed consent to participate and before any study specific screening procedures are performed.

Subjects who fail to meet eligibility criteria may not be rescreened for participation in the study, unless the condition that led to eligibility failure is transient, self-limited, and easily treatable, and is expected to be resolved at the time of dosing, as agreed by the investigator and medical monitor.

Six subjects will initially be randomly assigned in a 2:1 ratio to Cohort 1a, in a blinded fashion, to receive either a single 400-mg dose of ALXN1210 SC or single dose of placebo SC (Figure 1). The Safety Review Committee (SRC) will evaluate the first 48 hours of post-dose clinical safety data for subjects in Cohort 1a before enrollment into Cohorts 1b or 2 may begin. Thirty-six subjects will then be randomly assigned, in a 2:1 ratio, to either Cohort 1b (N=24) or Cohort 2 (N=12). Within Cohort 1b, the 24 subjects will further be randomly assigned, in a 5:1 ratio and blinded fashion, to receive either a single 400-mg dose of ALXN1210 SC or a single dose of placebo SC, respectively. The 12 subjects in Cohort 2 will receive a single 400 mg dose of ALXN1210 IV in an open-label fashion.

Figure 1: Study Diagram

Abbreviations: A = active drug; IV = intravenous; P = placebo; SC = subcutaneous; SRC = Safety Review Committee Note: The SRC will review the first 48 hours of post-dose safety data from Cohort 1a before enrollment into Cohorts 1b or 2 may begin.

At the sponsor's discretion, up to 8 additional subjects (2 subjects each in Cohorts 1a and 1b and 4 subjects in Cohort 2) may be enrolled into the study if 2 or more subjects discontinue within 3 months for reasons other than drug-related AEs, and after consultation with the SRC. All enrolled subjects will be included in analyses as appropriate. Subjects in Cohorts 1a and 1b will be combined for analyses. Subjects who withdraw from the study subsequent to dosing will be followed for safety assessments through the last scheduled study visit, if possible.

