3. NUMBER OF SUBJECTS AND RANDOMIZATION

3.2 Number and Source of Subjects

Forty-two subjects are planned for evaluation of the primary and secondary objectives in this study: 6 (4 ALXN1210 SC, 2 placebo SC) subjects in Cohort 1a; 24 (20 ALXN1210 SC, 4 placebo SC) subjects in Cohort 1b, and 12 (ALXN1210 IV) subjects in Cohort 2. At the sponsor's discretion, up to 8 additional subjects (2 subjects each in Cohorts 1a and 1b and 4 subjects in Cohort 2) may be enrolled into the study if 2 or more subjects discontinue within 3 months for reasons other than drug-related AEs, and after consultation with the Safety Review Committee (SRC).

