4.1. Analysis Populations

The safety population will consist of all subjects who receive the protocol-defined, single dose of study drug (ALXN1210 IV, ALXN1210 SC, or placebo SC). Subjects in this population will be used for the safety analysis.

The PK population will consist of all subjects from the safety population who received either ALXN1210 SC or ALXN1210 IV and who have sufficient serum concentration data to enable the calculation of PK parameters. The PK population will be used for PK summaries.

The PD population will consist of all subjects from the safety population who have sufficient total and free C5 concentration data and cRBC hemolysis data. The PD population will be used for PD summaries.

The immunogenicity analysis population will consist of all subjects from the safety population who have a pre-dose and post-dose ADA sample collected.

Inclusion and exclusion from each analysis set will be decided at the Blind Data Review Meeting prior to database lock.

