4.5 Pharmacokinetic Analysis

All serum concentration data will be listed for each individual subject and summarized at each time point by treatment group for ALXN1210-treated subjects.

If a Below the Level of Quantitation (BLQ) value occurs in a profile before the first measurable concentration, it will be assigned a value of zero concentration. If a BLQ value occurs after a measurable concentration in a profile and is followed by a value above the Lower Level of Quantitation (LLQ), then the BLQ will be omitted following visual inspection of the serum concentration versus time profile to assess the appropriateness of this assignment. If a BLQ value occurs at the end of a collection profile (after the last quantifiable concentration), the value will be treated as missing data. If 2 BLQ values occur in succession, the profile will be deemed to have terminated at the first BLQ value and any subsequent concentrations will be omitted from PK calculations.

Samples with no reportable value due to a bioanalytical issue or missing samples will be set to missing, and will not be included in the PK calculations.

When calculating the mean or median value for a concentration at a given time point, all BLQ values will be set to zero except when an individual BLQ falls between 2 quantifiable values, in which case it will be omitted.

For tabulation, graphical representation, and calculation purposes, all samples with no reportable value (or missing samples) observed after dosing will be set to missing.

Individual and mean concentrations versus nominal time on linear and semi-log scales will be presented graphically.

Individual serum concentration data for ALXN1210-treated subjects, with actual sampling dates and times calculated relative to the start of the infusion/injection, will be used to derive the PK parameters by non-compartmental analyses using Phoenix WinNonlin Version 6.3 or higher.

The following PK parameters will be derived:

Maximum observed serum concentration (C_{max})

- Time to maximum observed serum concentration (T_{max})
- Area under the serum concentration versus time curve from time zero to the last quantifiable concentration (AUC_t)
- Area under the curve from time zero to infinity (AUC_{∞})
- Terminal elimination rate constant (λ_z)
 - Only those data points that are judged to describe the terminal loglinear decline will be used in the regression.

Page 10 of 13

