4.9 Methods for Withdrawals, Missing Data, and Outliers

The individual serum concentration data and the actual timing of study drug administration and blood sampling will be used throughout the analyses. If there is any doubt about the actual time at which a sample was taken, then the scheduled time will be used. For PK data analysis, please see Section 4.5 regarding the handling of missing and BLQ values. For PD data analysis, there will be no imputation for missing values.

If medication dates are incomplete and it is not clear whether the medication was concomitant, it will be assumed to be concomitant.

AEs with unknown start date/time will be assumed to be treatment-emergent unless the end date/time is known to be before the first administration of study drug. Otherwise missing or partial dates will be listed as such.

There will be no further imputation of missing data (i.e., subjects who prematurely discontinue from the study will not be included in summary statistics or analyses beyond the time of discontinuation).

Depending on the extent of missing values, the appropriateness of the methods described for handling missing data may be reassessed prior to database lock (to examine the sensitivity of results to handling of missing data).

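### Must SAP 4.5.1 name which AUC ratio is F, and protect the AUCt ratio against early leavers from the IV arm?

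*SAP*

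**What the plan says.** Determining the absolute bioavailability of the SC form is a primary objective (Protocol 6.1, SAP 2.1). The one SAP section with that title, 4.5.1, states: "The geometric means ratio (ALXN1210 SC/ALXN1210 IV) and its 90% and 95% CI will be computed for the PK-parameters" Cmax, AUCt and AUC∞. The intervals come from log-transformed values with unequal variances. Protocol 18.7 lists the same three parameters, and the power statement in SAP 4.2 speaks only of a bioavailability ratio.

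SAP 4.5 defines AUCt as "Area under the serum concentration versus time curve from time zero to the last quantifiable concentration", so its end point is individual. The same section derives CL (IV) and CL/F (SC) from dose and AUC∞.

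On incomplete follow-up:

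- SAP 3.2 foresees exits: extra subjects "may be enrolled into the study if 2 or more subjects discontinue within 3 months for reasons other than drug-related AEs".
- SAP 4.9 uses leavers' data up to the exit: "subjects who prematurely discontinue from the study will not be included in summary statistics or analyses beyond the time of discontinuation".
- Protocol 8.1 adds: "All enrolled subjects will be included in analyses as appropriate".
- SAP 4.1 limits the PK population to treated subjects "who have sufficient serum concentration data to enable the calculation of PK parameters". Protocol 13.2 asks for enough PK samples to describe the profile.
- For the terminal slope, SAP 4.5 says: "Only those data points that are judged to describe the terminal loglinear decline will be used in the regression". It also accepts gaps: "Some PK parameters may not be calculated for all or some subjects if the concentration data are not deemed to be amenable to evaluation".

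**The concern.** A primary estimate should be recognisable before the data are seen. Two AUC ratios stand side by side under the bioavailability heading, and no sentence says which one answers the objective.

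The choice could matter. With a half-life of about 31 days, a subject whose last sample is on Day 29 has shown only about half of the exposure. With 12 IV subjects, each one carries a twelfth of the IV log mean, so a shortened IV AUCt lowers the denominator and raises the AUCt ratio. If that ratio were reported as F, early IV exits would make bioavailability look too high and its interval would cover too seldom. None of the rules on adequate data sets a numerical limit. A fully dosed subject who withdraws is promised only safety follow-up, where feasible (Protocol 8.1), so later PK samples are not assured.

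**Working it through.** **1. Which ratio is F.** From SAP 4.5, with 400 mg in both arms (SAP 3.3):

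- CL (IV) = 400 / AUC∞(IV)
- CL/F (SC) = 400 / AUC∞(SC)
- CL divided by CL/F = AUC∞(SC) / AUC∞(IV) = F

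The definitions therefore identify F as the AUC∞ ratio, which SAP 4.5.1 already tabulates with 90% and 95% intervals.

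**2. The plan's own figure.** SAP 4.2 gives F = 0.6, a lower limit of 0.4, CV 0.35, and 24 SC and 12 IV subjects. The log-scale SD is √ln(1 + 0.35²) = 0.340. The standard error is 0.340 × √(1/24 + 1/12) = 0.120. Then ln(0.6/0.4) / 0.120 − 1.645 = 1.73, a power of 95.8%. Simulating the unequal-variance interval gives 94.7%. The stated figure of more than 80% holds.

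**3. Size of the AUCt effect.** The half-life is 30.8 days at 400 mg (Protocol 5.1.1), so k = ln 2 / 30.8 = 0.0225 per day. Complete sampling runs to Day 200, which is 199 days. Mono-exponential IV decline is an assumption. A leaver's AUCt as a share of a completer's is

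f = (1 − e^(−k(Day − 1))) / (1 − e^(−199k)), with denominator 0.989.

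If m of 12 IV subjects leave, the ratio is multiplied by f^(−m/12). For a true F of 0.60:

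| Last IV sample | f | One leaver | Two leavers | 90% CI coverage, two leavers |
|---|---|---|---|---|
| Day 29 | 0.473 | ×1.064 = 0.64 | ×1.133 = 0.68 | 84% |
| Day 57 | 0.725 | ×1.027 = 0.62 | ×1.055 = 0.63 | 89% |
| Day 90 | 0.875 | ×1.011 = 0.61 | ×1.023 = 0.61 | 90% |

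- With one Day 29 leaver, coverage stays at 90%.
- If 10% or 20% of the IV area lies in a distribution phase, two Day 29 leavers give 0.666 or 0.655, with coverage 85.5% or 86.6%.
- Earlier exits move the ratio more: one at Day 15 gives 0.67 and one at Day 8 gives 0.70. Such profiles hold only 27% and 15% of the area and are the least likely to be judged adequate.
- At a true F of 0.40, the chance that the lower 90% limit of the AUCt ratio exceeds 0.4 rises from 5% to 9% with one Day 29 IV leaver and to 16% with two.

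**4. The opposite direction.** One SC leaver of 24 at Day 29 multiplies the ratio by 0.963 to 0.967 (assumed absorption rate 0.2 to 0.5 per day). Proportional Day 29 exits, 4 SC and 2 IV with all kept, give 0.584: slightly low, not high.

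**5. Complete follow-up.** Under the same assumptions the AUCt and AUC∞ ratios differ by less than 0.2%, so the choice is then immaterial.

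**6. Would a completeness limit help?** The log variance is 0.340² = 0.1156. Dropping n truncated IV profiles lowers mean squared error only if the log shortfall exceeds d = √(0.1156 × 12 / (n(12 − n))), which corresponds to an unobserved share above 1 − 0.989e^(−d). For n = 1, d = 0.355 and the share is 31%. For n = 2, d = 0.263 and the share is 24%. A limit of, say, 20% (an illustration, not in the documents) would therefore lose precision between 20% and those values.

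For AUC∞, dropping one Day 29 IV leaver gives an IV log-mean variance of 0.1156/11 = 0.0105. Keeping the subject gives between 0.0097 (five terminal points, 5% assay error) and 0.0096 + 0.197/144 = 0.0110 (three points, 10% error). Neither rule is better throughout.

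**The case for a change.** The strongest case for a change is that a primary estimate should be stated, not inferred. With two AUC ratios in the table, the choice formally stays open until results are known, and one sentence would close it. The rules on adequate data rest on judgement. They might also act unevenly: an SC leaver with slow absorption may lack the three points after Cmax needed for the terminal slope and be removed, while an IV leaver stays. Proportional exits would then no longer cancel, and the ratio would return to 0.68. Extra subjects do not cure this. With 14 IV subjects and both Day 29 leavers kept, the ratio is 0.668 with 85% coverage; with 16 it is 0.659 with 85.5%.

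Much of this stands. The label is missing, the arithmetic is right, and the rules are qualitative.

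The uneven-removal scenario is weaker. It reads SAP 4.1 as expelling any subject for whom one parameter cannot be calculated, whereas SAP 4.5 expects single parameters to be missing and explained in the study report. It also depends on an absorption rate that the documents do not give: the share of Day 29 SC profiles lacking three points runs from 10–22% at 0.4 per day to about 100% at 0.1 per day. Nor is it shown that a Day 29 IV leaver would be kept. Protocol 13.2 asks whether the samples describe the profile, and one that ends on Day 29 of a 200-day schedule could fail that test.

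The remaining harm needs someone to report the AUCt ratio as F against the plan's own clearance formulas, with the AUC∞ ratio in the same table and individual values listed.

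**Conclusion.** No change to the plan is needed. The missing label is a gap that a pharmacokinetic analyst fills from the SAP itself: at equal doses, CL over CL/F is the AUC∞ ratio. That ratio is already planned with its intervals, and nothing here shows it to be biased.

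The upward shift in the AUCt ratio is real but conditional. It is nil without early exits, about 1–2% for one or two IV leavers at Day 90, and 6% for one at Day 29 with coverage unchanged. It reaches 13% with 84% coverage only if two of 12 IV subjects are lost by Day 29, both are kept, and SC exits do not offset them. Exits before Day 29 would do more, but on profiles that are hardest to call adequate. These sizes assume mono-exponential decline, a 30.8-day half-life, F = 0.60 and CV 0.35; the documents give no dropout rate.

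A numerical limit on truncated or extrapolated area is a fair trade-off for the sponsor to settle before database lock. For AUCt it would affect only a supporting ratio and could raise the error with one or two leavers. For AUC∞ the gain or loss depends on assay error and the number of terminal points.
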